9.4.2.3. Handling of Withdrawal from Study and Missing HBsAg and HBV DNA Data

Two approaches will be used to determine a participant's response when HBsAg and HBV DNA data are missing from visits required to derive the primary endpoint.

- 1) For participants where wide disruptive events (such as COVID-19 pandemic) prevent assessment of the primary outcome, SVR will be imputed using all available data for participants for whom SVR can be assessed. For other participants where SVR in the absence of rescue medication cannot be ascertained due to missing data (withdrawal from the study or missing due to other reasons, but not due to a wide disruptive event), the participant will be assumed not to have achieved SVR (non-responder imputation).
- 2) For the primary estimands, a sensitivity analysis will be performed using the Bayesian model described in Section 9.4.3 assuming missing at random whereby a participant's response will be imputed using all available data (on and off treatment values) for participants who completed the study.

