4.2.2.1. Visit windowing and multiple measurements at one analysis timepoint

Visit windowing for the primary endpoint will be applied as specified in Table 2 and Table 3 and the windowed results will be used to determine the primary endpoint of SVR. Unscheduled assessments will be included in the analysis window. No imputation of missing data will be performed prior to visit windowing.

If there are multiple values within an analysis window the following rules will be applied:

For the End of '836 Treatment Analysis Timepoint:

1. The latest available assessment in the window will be selected.

For Post '836 Treatment Analysis Timepoints:

- 1. Worst non-missing value in the analysis window will be selected, if values are the same then the value closest to target day will be selected. If there are multiple values equidistant from the target day, the earliest will be selected. If all values within an analysis window are missing, then the result is missing for the analysis window.
- 2. Worst value is defined in the order of: highest actual value, then <LLOQ, and then TND.

Table 2 Primary endpoint analysis windows for Arms 1, 2 and 4

Analysis	Parameter	Target	Analysis	Window	Analysis	Protocol
Set / Domain	(if applicable)	Study Day	Beginning Timepoint	Ending Timepoint	Timepoint	Visit
Efficacy	HBsAg and HBV DNA	162	148	182	End of '836 Treatment	Week 24
		218	183	238	Post '836 treatment Week 8	Off treatment Week 8
		274	239	294	Post '836 treatment Week 16	Off treatment Week 16
		330	295	350	Post '836 treatment Week 24	Off treatment Week 24

Table 3 Primary endpoint analysis windows for Arm 3

Analysis	Analysis Parameter		Analysi	s Window	Analysis	Protocol
Set / Domain	(if applicable)	Study Day	Beginning Timepoint	Ending Timepoint	Timepoint	Visit
Efficacy	HBsAg and HBV DNA	78	64	98	End of '836 Treatment	Week 12
		134	99	154	Post '836 treatment Week 8	Week 20
		190	155	210	Post '836 treatment Week 16	Off treatment Week 4
		246	211	266	Post '836 treatment Week 24	Off treatment Week 12

The primary analysis will be based on planned end of treatment regardless of whether a patient discontinued treatment early.

For the second supplementary estimand described in Section 4.2.4.2, SVR will be measured from actual rather than planned end of treatment and the analysis windows should be amended accordingly. For this estimand, the date of last dose should be treated as the reference date and the rules in Table 4 should be used to determine the endpoint of SVR.

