4.2.2.2. Intercurrent Events and Missing data

The intercurrent event of use of rescue medication has been incorporated into the definition of variable (composite strategy). The intercurrent event of discontinuation of, interruption of, and adherence to IP not due to wide disruptive event will be ignored (treatment policy).

To prevent the efficacy of GSK3228836 being penalized for uncontrollable and unusual events (i.e. wide disruptive events such as the COVID-19 pandemic), if a wide disruptive event leads to discontinuation of GSK3228836 or significant interruption/non-adherence to GSK3228836, this will be handled assuming the intercurrent event had not happened (hypothetical strategy). Significant interruption/non-adherence is defined as a gap of >=21 days between treatment doses at any time during the on-treatment period. According the hypothetical strategy, any data collected after the intercurrent event will be set to missing.

If all analysis windows have non-missing response information, a participant's response (Responder or Non-responder) is determined as follows:

- 1. If rescue medication was used, then the participant is a non-responder.
- 2. If HBsAg <LLOQ and HBV DNA <LLOQ in each of the analysis window, then the participant is a Responder, otherwise the participant is non-responder. Note: A result of TND is considered as <LLOQ.

The following approach will be used to determine a participant's response when HBsAg and HBV DNA data are missing from visits required to derive the primary endpoint:

For participants where wide disruptive events (such as COVID-19 pandemic) prevent assessment of the primary outcome, SVR will be imputed using all available data for

participants for whom SVR can be assessed. The final inference from the hierarchical Bayesian model will account for the missing data assuming MAR. For other participants where SVR in the absence of rescue medication cannot be ascertained due to missing data (withdrawal from the study or missing due to other reasons, but not due to a wide disruptive event), the participant will be assumed not to have achieved SVR (non-responder imputation).

After the imputation above, if there is missing data in at least one analysis window then the participant is a non-responder.

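### The closing missing-data sentence of SAP 4.2.2.2 does not exempt wide disruptive events and, read literally, overrides the MAR handling set out just before it

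*SAP*

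**What the plan says.** SAP 4.2.2.2 deals with primary-endpoint response in stages.

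- **Disruptive event as intercurrent event.** If it leads to stopping GSK3228836, or to a gap of at least 21 days between doses, a hypothetical strategy applies and "any data collected after the intercurrent event will be set to missing". The stated purpose is "To prevent the efficacy of GSK3228836 being penalized for uncontrollable and unusual events".
- **All windows non-missing.** Rescue use makes the participant a non-responder. Otherwise, response requires both markers below LLOQ in every window.
- **Missing because of a disruptive event.** Where such events "prevent assessment of the primary outcome, SVR will be imputed using all available data for" participants with assessable SVR, the stated mechanism is: "The final inference from the hierarchical Bayesian model will account for the missing data assuming MAR".
- **SVR not ascertainable because of other missing data.** Non-responder imputation.
- **Closing sentence.** "After the imputation above, if there is missing data in at least one analysis window then the participant is a non-responder".

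On windowing, SAP 4.2.2.1 says: "No imputation of missing data will be performed prior to visit windowing". Protocol 9.4.2.3 makes the same split ("For participants where wide disruptive events (such as COVID-19 pandemic) prevent assessment of the primary outcome, SVR will be imputed", with non-response for the rest) but has no closing sentence. SAP 4.8 does not list that sentence as a change from the protocol. SAP 4.3.1.1, on response at end of treatment, confines non-response to missing data without a disruptive cause and says that this follows the primary endpoint.

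**The concern.** The MAR step and the closing sentence work at different levels. The first concerns SVR, one outcome per participant. The second looks at individual analysis windows. A participant whose later data were set to missing, or never collected, because of a disruptive event can have SVR handled by the model and still have empty windows. The closing sentence then applies to that participant, with no exemption.

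Programmed as written, this replaces the hypothetical strategy of the primary estimand (SAP 4.2.1) with treatment as failure for these participants. The comparisons of arms 1 to 3 and the regimen selection in SAP 4.3.1.2 use the same SVR variable, so they would inherit the result. Two competent programmers could derive different primary results from this section.

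**Working it through.** **Order of operations for one affected participant.** Suppose a disruptive event stops dosing at mid-treatment.

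1. Data after the event are set to missing, so later windows are empty.
2. The rules for complete windows do not apply.
3. SVR is imputed, or integrated over in the model, under MAR. No step is stated that puts HBsAg or HBV DNA values into the windows.
4. The closing sentence asks whether any window is missing. The answer is yes, so the literal result is non-response.

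Step 4 contradicts step 3, the stated aim, SAP 4.2.1, protocol 9.4.2.3 and the split in SAP 4.3.1.1.

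**Reproducing the plan's figures.** Inputs from SAP section 5: 66 per arm in arms 1 to 3, a Beta(0.5, 0.5) prior, and a criterion of 75% posterior probability that the rate exceeds a threshold. The minimum count is the smallest r with P(p > threshold | Beta(r + 0.5, 66 − r + 0.5)) > 0.75. The chance of meeting the criterion is then the binomial upper tail.

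- Threshold 15%: r = 12; 69.1% at a true rate of 20% (SAP Table 11: 69%).
- Threshold 20%: r = 16; 87.7% at a true rate of 30% (SAP Table 11: 88%).

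Both reproduce. They assume no missing data, so this point does not make them wrong.

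**Shift in the estimate.** The proportion affected is an assumption, because the documents give none. With 20% SVR in the rest, the literal rule gives 0.95 × 20% = 19.0% at 5% affected and 0.90 × 20% = 18.0% at 10%. In counts, the expected rate is 20% × (66 − m)/66, which is 19.1%, 18.5% and 17.9% for m = 3, 5 and 7. The rule adds to the denominator but never to the numerator, so it cannot raise the rate.

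**Effect on the criterion.** This uses the unstratified Beta-binomial behind SAP Table 11, not the hierarchical model. MAR is represented by dropping the m affected participants; the literal rule counts them as failures out of 66. Responders arise among the 66 − m assessed in both cases.

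| m of 66 | True rate / threshold | MAR: needed, chance | Literal: needed, chance |
|---|---|---|---|
| 3 (4.5%) | 20% / 15% | 12 of 63, 62.5% | 12 of 66, 62.5% |
| 5 (7.6%) | 20% / 15% | 11 of 61, 69.9% | 12 of 66, 57.6% |
| 7 (10.6%) | 20% / 15% | 11 of 59, 65.4% | 12 of 66, 52.6% |
| 3 (4.5%) | 30% / 20% | 15 of 63, 88.9% | 16 of 66, 82.4% |
| 5 (7.6%) | 30% / 20% | 15 of 61, 85.7% | 16 of 66, 78.1% |
| 7 (10.6%) | 30% / 20% | 14 of 59, 88.6% | 16 of 66, 73.0% |

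The MAR column is uneven because the required count moves in whole participants.

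**One data set, two answers.** Take 11 responders among 61 assessed, plus 5 affected.

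- MAR: Beta(11.5, 50.5), mean 11.5/62 = 18.5%, P(rate > 15%) = 75.4%. Criterion met.
- Literal: Beta(11.5, 55.5), mean 11.5/67 = 17.2%, P(rate > 15%) = 66.0%. Criterion not met.

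**The case against.** A reader might infer that the plan makes every participant with a missing window a failure and so plainly cancels the MAR handling. The documents do not support that, for three reasons.

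- The sentence operates only after the imputation step. It can be read as a residual rule for participants whose response is still undetermined, which leaves MAR-handled participants alone. The purpose statement, protocol 9.4.2.3 and SAP 4.3.1.1 all favour that intent.
- The mechanics are not fully specified. SAP 4.2.2.1 rules out imputation only before windowing, so filling windowed results afterwards is not excluded. The statement that the model accounts for the missing data points to participant-level handling but does not settle it.
- Participants affected by disruptive events are not the only group the sentence can reach. Someone with rescue use, or a marker at or above LLOQ in one window, and a missing window elsewhere is not covered by the complete-window rules. Nor is that person's SVR unascertainable: it is a known failure. Only the closing sentence classifies such a participant, and it does so correctly.

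All three stand, and the third constrains the fix. The assumed shift of 1 to 2 points is also small beside the 10% to 28% credible interval that SAP Table 10 gives for 12 of 66, and with 3 affected the 20%/15% case does not change. The conflict remains, because the sentence tests for missing windows, not for undetermined SVR, and that is what a programmer would code. The MAR sensitivity analysis in SAP 4.2.3 covers all missing data, so it would not isolate the issue.

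**Conclusion.** The concern holds as a contradiction or ambiguity in a primary-endpoint rule. Read literally, the closing sentence overrides the MAR handling of wide disruptive events and departs from the hypothetical strategy. A reading that avoids the conflict exists, but the text does not say which applies.

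Under the literal rule the SVR rate moves downward: from 20% to 19.0% or 18.0% if 5% or 10% of an arm is affected. Those proportions are assumptions, and with few affected the decision may not change. The decision figures also rest on the unstratified model, which the SAP expects to behave similarly to the hierarchical one. Because the two readings can give opposite results on the 75% criterion, the wording should be settled before the primary SVR variable is derived.

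**What to change.** Replace the closing sentence of SAP 4.2.2.2 with:

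> Participants with rescue medication use, or with HBsAg or HBV DNA ≥LLOQ in any window retained after the hypothetical-strategy step, are non-responders regardless of other missing windows. Otherwise, participants with a missing window not due to a wide disruptive event are non-responders; participants whose SVR cannot be assessed because of a wide disruptive event keep SVR as missing and are handled under MAR in the model.

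Deleting the sentence, or only limiting it to missing windows without a disruptive cause, is not enough. Either would leave unclassified a participant with an observed failure in one window and a disruptive-event gap in another.

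The cost is this replacement text and a matching line in the programming specification. No new data, analysis or sample-size work is needed, and the rule then agrees with protocol 9.4.2.3 and SAP 4.2.1.

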4.2.2.3. Model Checking & Diagnostics - MCMC Mixing Diagnosis

Two sampling chains will be run, with differing starting values and each with a burn-in period of 5,000 samples, to ensure adequate sampling from the posterior. The starting values will be as above Section 4.2.2.

Mixing will be regarded as "each chain is independently realizing values similar to those for which the other chains have also sampled." Adequate mixing will be concluded if the chains meet following conditions:

- 1. The Brooks-Gelman Ratio (BGR) (Brooks SP, 1998) for each parameter is in the interval (0.8, 1.2).
- 2. Each chain appears mix well, upon visual inspection of each chain's trace plot, including assessing the mutual overlap of the chains for each parameter.
- 3. Each kernel density plot appears smooth upon visual inspection.

4.2.3. Sensitivity analyses

For the primary estimand, a sensitivity analysis will be performed using the Bayesian model described in Section 4.2.2, assuming missing at random whereby a participant's response will be imputed using all available data (on and off-treatment values) for participants who completed the study.

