4.2.2. Main analytical approach

The participant population (on nucelos(t)ide treatment or not currently on nucleos(t)ide treatment) will not be included as a stratification factor in the analysis model, as each population will be analyzed separately.

A Bayesian hierarchical model will be fitted using MCMC methods, and will be used to estimate the posterior probability of sustained virologic response rate for each arm incorporating the baseline analysis stratification factors (Table 1) [Jones, 2011].

Model for each arm:

Number of responders
$$r_q \sim Binomial(n_q, p_q)$$
, $g = 1, 2, 3, 4$

$$\theta_g = logit(P_g) = log\left(\frac{P_g}{1 - P_g}\right) = \gamma_0 + \gamma_1 I_{\{B1+\}} + \gamma_2 I_{\{B2+\}} + \psi_g, \qquad g = 1, 2, 3, 4$$

Where $\gamma_0, \gamma_1, \gamma_2, \psi_g$ are all parameters. Thus,

$$\theta_1 = \, \gamma_0 + \, \psi_1$$

$$\theta_2 = \gamma_0 + \gamma_1 + \psi_2$$

$$\theta_3 = \gamma_0 + \gamma_2 + \psi_3$$

$$\theta_4 = \gamma_0 + \gamma_1 + \gamma_2 + \psi_4$$

Priors:

$$\gamma_k \sim Normal(0, 10^6), k = 0, 1, 2$$

$$\psi_g \sim Normal(0,\omega^2\,), g=1,2,3,4$$

$$\omega \sim Half - normal(1)$$

Where we define r_g as the number of SVR responders among n_g participants, p_g as SVR rate $\frac{r_g}{n_g}$, θ_g as the log odds of treatment response $\log(\frac{p_g}{1-p_g})$, index g=1,...,4 refers to the analysis stratum number, γ_k represent fixed effects of baseline analysis stratification factors (see below), and ψ_g denotes a random effect in analysis stratum g.

The four analysis strata and representation of the two baseline analysis stratification factors B_1 and B_2 in the model are shown in Table 1.

Stratum	B_1 : HBsAg ($I_{\{B1+\}}$)	B_2 : HBeAg $(I_{\{B2+\}})$
1: HBsAg ≤3 log IU/mL and Negative HBeAg	B₁- (< 3 log IU/mL) (0)	B ₂₋ (Negative) (0)
2: HBsAg >3 log IU/mL and Negative HBeAg	B ₁₊ (>3 log IU/mL) (1)	B ₂₋ (Negative) (0)
3: HBsAg ≤3 log IU/mL and Positive HBeAg	B₁- (< 3 log IU/mL) (0)	B ₂₊ (Positive) (1)
4: HBsAg >3 log IU/mL and Positive HBeAg	B ₁₊ (>3 log IU/mL) (1)	B ₂₊ (Positive) (1)

For each arm, the posterior distribution of SVR rate P(pg|data), g=1,2,3,4 will be derived for each analysis stratum using the model specified above.

$$P(p_1|data) = P(\frac{e^{\theta_1}}{1 + e^{\theta_1}}|data)$$

$$P(p_2|data) = P(\frac{e^{\theta_2}}{1 + e^{\theta_2}}|data)$$

$$P(p_3|data) = P(\frac{e^{\theta_3}}{1 + e^{\theta_3}}|data)$$

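### The missing-at-random sensitivity analysis is said to draw on on- and off-treatment values, but the only model named for it contains baseline strata alone, so a dropout's own virology is ignored

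*SAP*

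**What the plan says.** SAP 4.2.3 states that, for the primary estimand, "a sensitivity analysis will be performed using the Bayesian model described in Section 4.2.2, assuming missing at random", and that the missing response will be "imputed using all available data (on and off-treatment values) for participants who completed the study". Protocol 9.4.2.3 has the same rule: "a participant's response will be imputed using all available data (on and off treatment values) for participants who completed the study". Neither document sets out a separate imputation model.

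The model in SAP 4.2.2 is binomial for responder counts in four strata within each arm, and it "will be used to estimate the posterior probability of sustained virologic response rate for each arm incorporating the baseline analysis stratification factors". On the logit scale it has an intercept, an indicator for baseline HBsAg above 3 log IU/mL, an indicator for positive HBeAg, and a stratum random effect. The coefficients "represent fixed effects of baseline analysis stratification factors (see below". There is no term for any post-baseline value.

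In the primary analysis, SAP 4.2.2.2 splits missing data by cause. Where a wide disruptive event prevents assessment, SVR is imputed and "The final inference from the hierarchical Bayesian model will account for the missing data assuming MAR". For other missing data, "the participant will be assumed not to have achieved SVR (non-responder imputation)".

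**The concern.** The sensitivity analysis describes a use of data that the named model cannot deliver for the participant being imputed. A model of outcome on strata cannot tell a dropout last seen with HBsAg below LLOQ from one last seen at 1000 IU/mL.

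The missing-at-random assumption is only as good as what is conditioned on. SVR requires both markers below LLOQ in every window, so virology during and after treatment should carry much information about it. The SAP itself plans positive and negative predictive values of on-treatment response for SVR (4.4.1.2 and 4.6.3). HBsAg and HBV DNA are measured at every weekly dosing visit, apart from the Day 4 and Day 11 loading-dose visits. Conditioning on strata alone leaves this information unused.

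At stake is what the sensitivity analysis can show. If participants who leave are mostly those not responding, the estimate is too high. A reader could then take a figure above the primary one as reassurance, when part of it is response credited to people who showed no sign of it.

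**Working it through.** **Inputs from the documents.** About 66 participants per arm in arms 1–3 of each population; Beta(0.5, 0.5) prior for the operating characteristics; criterion of posterior P(rate > 15%) above 75% (SAP section 5); model and priors from SAP 4.2.2. The documents state no dropout rate. Dropout numbers, stratum sizes and responder counts below are assumptions.

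**1. Reproducing the plan's figure.** The smallest r for which Beta(r + 0.5, 66 − r + 0.5) puts more than 75% of its mass above 0.15 is r = 12 (0.771; r = 11 gives 0.660). P(X ≥ 12) for Binomial(66, 0.20) is 0.691. SAP Table 11 gives 12 responders and 69%, so the figures agree.

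**2. What the named model does with a missing SVR.** Let stratum g of an arm have n_g participants, of whom m_g have a missing outcome. Under missing at random the missing outcomes integrate out of the likelihood. This leaves r_g ~ Binomial(n_g − m_g, p_g). Each missing SVR is then a draw with probability p_g from that posterior, identical for everyone in the same arm and stratum. The last HBsAg does not enter.

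**3. Simple arithmetic.** Assume 10% missing and completer SVR of 20%. Among dropouts, assume 80% had quantifiable HBsAg at the last visit (SVR chance 0) and 20% were below LLOQ (SVR chance 60%).
- Strata-only, missing at random: 0.9 × 20 + 0.1 × 20 = 20.0%
- Using own data: 0.9 × 20 + 0.1 × (0.2 × 60) = 19.2%
- Non-responder imputation: 0.9 × 20 + 0.1 × 0 = 18.0%

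The gap between the first two is 0.8 points, or 0.008 × 66 ≈ 0.5 of a participant.

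**4. An extreme case near the criterion.** Assume an arm of 66 with strata of 16/26/8/16 and 11 observed responders (5/4/1/1), and let every dropout be a true failure. Scoring them so is the same as non-responder imputation. The 4.2.2 model was fitted by MCMC (two chains, agreeing within 0.01). The last column is the unstratified check, P(rate > 15%) under Beta(11.5, 55.5 − m).

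| Missing m | SVR, 4.2.2 model | P(>15%), 4.2.2 model | P(>15%), Beta check |
|---|---|---|---|
| 0 (all dropouts scored as failures) | 16.7% | 0.62–0.63 | 0.660 |
| 3 | 17.5% | 0.69–0.70 | 0.718 |
| 7 | 18.9% | 0.78 | 0.788 |
| 13 | 20.6% | 0.86–0.87 | 0.877 |

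With 7 missing (2/3/1/1 by stratum), the imputed probabilities are about 0.36/0.18/0.15/0.07. The raw completer rates are 5/14, 4/23, 1/7 and 1/15, or 0.357/0.174/0.143/0.067. The model therefore reproduces the complete-case rates and credits about 1.45 responders to the 7 dropouts.

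**The case against.** **The wording can be reconciled.** The text speaks of values from participants who completed the study. Completers' SVR is itself derived from on- and off-treatment measurements, so those values reach the 4.2.2 model through the outcome. A separate imputation step might also be intended. This stands against reading the two statements as flatly contradictory, a stronger reading the text does not force. It does not supply an imputation model: on the first reading the dropout's own data are still unused, and the second is not written down.

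**The primary result.** A reader might infer that the primary analysis is biased upwards. The documents do not support that. Missing at random applies there only to wide disruptive events, an external cause, and nothing suggests that those participants respond less well. Under the inputs of step 3, 20/60 = 33.3% of completers would be below LLOQ. If disrupted participants resemble them, using own data gives 0.9 × 20 + 0.1 × (0.333 × 60) = 20.0%, the same as the strata-only figure. Other missing data are handled by non-responder imputation.

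**Observed failures.** A reader might also infer that a participant with a quantifiable post-treatment result would be imputed as a possible responder. SAP 4.2.2.2 imputes where SVR cannot be assessed, and one windowed failure settles SVR, so a careful programmer would score non-response. This largely stands. However, that section classifies from observed values only when all windows are present, and 4.2.3 has no rule for partly missing windows.

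**Size.** The inputs are assumed and the 0.8-point shift is small beside the 10%–28% interval the SAP shows for 12 of 66. A zero chance of SVR is too harsh for early dropouts, since everyone enters with HBsAg above 100 IU/mL. Step 4 is an extreme, and 4.2.3 attaches no decision rule to the sensitivity analysis. All of this stands.

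**Conclusion.** The point holds for the sensitivity analysis. As written, it imputes at the completers' arm-and-stratum rate and ignores the participant's own virology. It is therefore close to a complete-case analysis and can overstate SVR if dropouts respond less well. For disruptive events in the primary analysis the finding is narrower: the same baseline-only model discards available information, with no bias shown.

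The size is illustrative because no dropout rate is given: 20.0% against 19.2% under the inputs of step 3. In the extreme case with 11 responders and 7 dropouts who all fail, P(rate > 15%) is 0.78 rather than 0.62–0.63 (0.79 rather than 0.66 unstratified), on either side of 75%. The gap can thus matter near the criterion but is otherwise modest. This is a low-cost improvement to the plan and does not call the main result into question.

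**What to change.** Amend SAP 4.2.3, and 4.2.2.2 where it relies on the same model, in two steps.

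1. State who is not imputed. A participant is a non-responder if rescue medication was used, or if a windowed result selected by the 4.2.2.1 rules is at or above LLOQ. Those rules take the latest value in the end-of-treatment window and the worst value in post-treatment windows. Exclude values set to missing under the hypothetical strategy. A blanket rule that any quantifiable value in a window means failure should be avoided, because it would override the latest-value rule and undo the hypothetical strategy.
2. For the rest, multiply impute SVR from a model with arm, baseline strata, and last retained HBsAg and HBV DNA status together with its timing. Timing is needed because a quantifiable value early in treatment does not mean the same as one at its end. Then fit the 4.2.2 model to each completed data set and pool the posterior draws.

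The cost is SAP wording and modest programming; the measurements are already scheduled. The sensitivity estimate may come out slightly lower.
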